4.4.1.1 Gastrointestinal Disorders

The most common non-hepatobiliary GI AEs reported in clinical studies with cabozantinib regardless of causality are diarrhea, nausea, decreased appetite, vomiting, constipation, stomatitis and abdominal pain. Diarrhea, nausea, and vomiting were amongst the most common adverse reactions experienced by $\geq 20\%$ of subjects who took erlotinib.

Diarrhea: Subjects should be instructed to notify their physician immediately at the first signs of poorly formed or loose stool or an increased frequency of bowel movements.

Guidelines for the evaluation and management of diarrhea are shown in Table 4-4.

Administration of antidiarrheal/antimotility agents is recommended at the first sign of diarrhea as initial management. Some subjects may require concomitant treatment with more than one antidiarrheal agent. When therapy with antidiarrheal agents does not control the diarrhea to tolerable levels, cabozantinib and erlotinib should be temporarily interrupted or dose reduced. When the diarrhea is controlled, retreatment with cabozantinib and erlotinib may be acceptable per investigator decision.

In addition, general supportive measures should be implemented such as continuous oral isotonic hydration, correction of fluid and electrolyte abnormalities, small frequent meals, and stopping lactose-containing products, high-fat meals, and alcohol.

Recurrent or prolonged diarrhea can be associated with anal or perianal skin erosions which increase the risk for anal abscesses, fistulas, or proctitis. Good personal hygiene should be emphasized. Regular examinations of the perianal region should be performed whenever diarrhea has occurred during treatment with cabozantinib and erlotinib. Infections of the perianal region should be treated per local guidelines.

CONFIDENTIAL

Table 4-4: Management of Treatment-Emergent Diarrhea

| CTCAE v.4.03 Grade | Action To Be Taken |
|---|--|
| Tolerable Grade 1-2 (duration < 48 h) | 
 • Continue with study treatment and consider dose reduction • Initiate treatment with an antidiarrheal agent (eg, loperamide 4 mg followed by 2 mg after each episode of diarrhea [maximum: 16 mg loperamide per day]) • Dietary modifications (eg, small lactose-free meals, bananas and rice) • Intake of isotonic fluids (1-1.5 L/day) • Re-assess after 24 hours: 
 ○ Diarrhea resolving to baseline bowel habits: gradually add solid foods and discontinue or decrease antidiarrheal treatment after 12 h diarrhea-free interval ○ Diarrhea not resolving: Continue/resume antidiarrheal |
| Intolerable Grade 2, Grade 2 > 48 h, or ≥ Grade 3 | 
 • Interrupt study treatment • Ask subject to attend clinic • Rule out infection (eg, stool sample for culture) 
 ○ Administer antibiotics as needed (eg, if fever or Grade 3-4 neutropenia persists > 24 h) • Administer fluids (1-1.5 L/day orally or IV, as appropriate) for hydration or to correct electrolyte abnormalities • For Grade 3-4 or complicated lower grade diarrhea consider hospitalization and IV hydration • Re-assess after 24 h 
 ○ Diarrhea resolving to baseline bowel habits or Grade ≤ 1: consider restarting study treatment at reduced dose ○ Diarrhea not resolving: 
 • Start and or continue antidiarrheal treatment (eg, loperamide 4 mg followed by 2 mg after each episode of diarrhea [maximum: 16 mg loperamide per day]) • Consider starting second line antidiarrheal or referral to gastroenterologist ○ If severe diarrhea cannot be resolved with the measures listed above, discontinue treatment. |

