Table 4-2: Dose Reductions of Cabozantinib and Erlotinib

| Assigned Starting Dose | First Dose Level Reduction |
|-------------------------------|---|
| 40-mg cabozantinib oral qd | 20-mg cabozantinib oral qd (discontinue if this dose is not tolerated) |
| 100-mg erlotinib oral qd | 50-mg erlotinib oral qd (discontinue if this dose is not tolerated) |

See Section 4.5.5 for complete details regarding potential drug interactions.

CONFIDENTIAL

Table 4-3: Dose Modifications for Treatment-Related AEs for Cabozantinib and Erlotinib

Dose modifications should be made to both cabozantinib and erlotinib for any overlapping treatment-related adverse events unless the investigator suspects one drug over another to be the cause of unacceptable toxicity. In this case, dose modifications may be made to one drug per the investigator's discretion. The most common overlapping toxicities are: diarrhea, fatigue, nausea, skin reactions and vomiting.

| CTCAE v.4.03 Grade | Recommended Guidelines for Management^a |
|--|---|
| Grade 1 AEs | Add supportive care as indicated. Continue treatment at the current dose level if AE is manageable and tolerable. |
| Grade 2 AEs which are tolerable and are easily managed | Continue treatment at the current dose level with supportive care. |
| Grade 2 AEs which are intolerable and cannot be adequately managed | At the discretion of the investigator, treatment should be dose reduced or interrupted. Note: It is recommended that dose holds be as brief as possible. |
| Grade 3 AEs (except clinically non-relevant laboratory abnormalities) | Treatment should be interrupted unless the toxicity can be easily managed with a dose reduction and optimal medical care. Note: It is recommended that dose holds be as brief as possible. |
| Grade 4 AEs (except clinically non-relevant laboratory abnormalities) | Subjects should have treatment interrupted immediately. Discontinue treatment unless the following criteria are met: 
 • Subject is deriving clear clinical benefit as determined by the investigator and agreed by the sponsor-investigator • Toxicity can be managed with a dose reduction following recovery to Grade 1 (or baseline) and optimal medical care |

Note: The dose delay and modification criteria for specific medical conditions are provided in Section 4.3.1. For re-treatment criteria of study treatment after a dose hold see Section 4.3.2.

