4.4.1.17 Renal Failure

Hepatorenal syndrome, severe acute renal failure including fatal cases, and renal insufficiency can occur with erlotinib treatment. Renal failure may arise from exacerbation of underlying baseline hepatic impairment or severe dehydration. Withhold treatment in subjects developing severe renal impairment (CTCAE version 4.03 grade 3 or 4) until renal toxicity is resolved.

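### Tables 4-3 and 4-4 give different dose actions for treatment-related Grade 4 diarrhea and for prolonged but tolerable Grade 2 diarrhea, and no sentence says which table prevails

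*Combined protocol and SAP*

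**What the plan says.** **Table 4-3 (Section 4.3.1)** sets dose modifications for treatment-related adverse events. Its footnote extends it to events of unclear relationship, and its introduction lists diarrhea among the toxicities that the two drugs share.
- Grade 2, tolerable and easily managed: stay on the current dose with supportive care. No time limit is given.
- Grade 2, intolerable: reduce or interrupt, at the investigator's discretion.
- Grade 3: "Treatment should be interrupted unless the toxicity can be easily managed with a dose reduction and optimal medical care".
- Grade 4: interrupt at once, then discontinue unless two criteria hold. The first is "Subject is deriving clear clinical benefit as determined by the investigator and agreed by the sponsor-investigator". The second is that, after recovery to Grade 1 or baseline, a dose reduction with medical care can contain the event.

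**Section 4.4.1.1 and Table 4-4** deal with treatment-emergent diarrhea.
- The text says: "When therapy with antidiarrheal agents does not control the diarrhea to tolerable levels, cabozantinib and erlotinib should be temporarily interrupted or dose reduced". Once diarrhea is controlled, it leaves retreatment to the investigator.
- The upper row of Table 4-4 covers tolerable Grade 1-2 lasting under 48 hours.
- The lower row covers "Intolerable Grade 2, Grade 2 > 48 h, or ≥ Grade 3". Its first action is "Interrupt study treatment". On recovery to baseline bowel habits or Grade 1 or lower, the site may "consider restarting study treatment at reduced dose". The stopping rule is "If severe diarrhea cannot be resolved with the measures listed above, discontinue treatment".

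**Cross-references.** Section 4.3.1 points to Section 4.4.1 for specific events without saying that it overrides Table 4-3. The note under Table 4-3 sends the reader, for specific conditions, to Section 4.3.1, which is the section the table sits in. Section 4.3.2 allows restart at a reduced dose after recovery from a possibly related toxicity and sets no separate condition for Grade 4.

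**The concern.** Diarrhea is the leading toxicity that the protocol reports for this combination, and two sets of instructions cover it. For a Grade 4 event the two differ in the default (stop, or consider restarting), in the conditions for restarting, and in who must agree. A patient could be re-exposed after a Grade 4 event under one table without the agreement that the other requires.

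There is also a consequence for the data. Tolerability is a secondary objective. Section 8.7 tabulates significant violations of the treatment plan, and Section 8.4.3 removes patients with significant violations from the efficacy population. With two rules in force, whether a given hold, reduction or restart departs from the plan is not defined.

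**Working it through.** The protocol states no figure on this point, so the check is a comparison by grade. It is confined to diarrhea that both tables cover, which is diarrhea judged related or of unclear relationship.

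| Diarrhea | Table 4-3 | Table 4-4 | Can one action satisfy both? |
|---|---|---|---|
| Grade 2, tolerable and easily managed, over 48 h | Continue at current dose | Interrupt | No |
| Grade 2, intolerable | Reduce or interrupt | Interrupt | Yes, by interrupting; the option to reduce is missing from Table 4-4 |
| Grade 3 | Interrupt, unless easily managed by reduction | Interrupt | Yes, by interrupting; the exception is missing from Table 4-4 |
| Grade 4, recovered to Grade 1 or baseline | Discontinue unless both criteria are met | Restart at reduced dose may be considered; discontinue only if unresolved | Only if the Table 4-3 criteria are read into Table 4-4, which does not mention them |

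**Grade 4.** Take a patient whose Grade 4 diarrhea recovers but for whom no clear benefit has been agreed. Table 4-3 says discontinue. Table 4-4 permits restart, and the Section 4.4.1.1 text leaves that to the investigator. This case could be common. Section 4.4 says that diarrhea tends to begin early (with erlotinib, usually within a month), while Section 6.3.1.8 places the first on-treatment scan at Cycle 3 Day 1, which is day 2 × 28 + 1 = 57. Benefit need not be radiographic, but the question will often arise before any on-treatment image exists.

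**Inside Section 4.4.1.1.** For diarrhea not controlled to tolerable levels, the text offers interruption or reduction, while Table 4-4 offers only interruption for intolerable Grade 2 and for Grade 3 and above. Giving Table 4-4 precedence over Table 4-3 would not resolve this.

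**Scale of the Grade 3 difference.** The inputs are 29% Grade 3 diarrhea with the combination in lung cancer (Section 2.1), and 37 patients for the test with up to 40 enrolled (Section 8.5). Expected cases = rate × n:
- 0.29 × 37 = 10.7
- 0.29 × 40 = 11.6

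Only cases easily managed by reduction are treated differently by the two tables, so about 11 of 37 is an upper bound for Grade 3. It assumes that the lung cancer rate carries over to this population and dose. No rate is given for intolerable Grade 2, prolonged Grade 2 or Grade 4, so those parts cannot be sized.

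**The case against.** The best defence is that the specific table governs. Section 4.3.1 points to Section 4.4.1 for specific events, and Section 4.4.1 assigns diarrhea to Table 4-4. Where the authors want Table 4-3 to apply they say so, as for fatigue (4.4.1.4) and for rash other than hand-foot syndrome (4.4.1.5). The mention of diarrhea in the introduction to Table 4-3 concerns whether to modify one drug or both. This is a natural reading, but it is nowhere stated, the note under Table 4-3 points back to its own section, and it leaves Section 4.4.1.1 at odds with its own table.

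A second defence is that the tables can be read together. Both interrupt at Grade 4, both look for recovery to Grade 1 or baseline, and both restart at a lower dose. Table 4-4 says only that restart may be considered, and the guidance column of Table 4-3 is headed as recommended. Section 4.3.1 also allows dose action at lower grades than Table 4-3 defines. In addition, this is a single-site trial with weekly review meetings that include the principal investigator and cover dose adjustments (Section 9). These points lower the chance of unnoticed re-exposure. They do not give a site one stated rule, and discretion to interrupt prolonged Grade 2 is not the same as the instruction to do so in Table 4-4.

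A third point is that Section 8.8 plans no analysis of dose actions as such, so the effect on reported results is indirect. That stands.

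**Conclusion.** The tables conflict on two points: the conditions for restarting after Grade 4 diarrhea, and Grade 2 that is tolerable and easily managed beyond 48 hours. The Grade 2 conflict requires both conditions; prolonged Grade 2 that is not easily managed falls outside the Table 4-3 row that says continue. The difference for Grade 3 and intolerable Grade 2 is lesser, being a missing option rather than a contradiction.

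The conclusion rests on the wording of the tables and on the absence of a precedence rule. The only number, at most about 11 of 37, belongs to the Grade 3 part of the lesser point and depends on the lung cancer rate. The two-stage design (11 then 37 patients, error rates 0.045 and 0.198) is untouched. Severity: should-fix.

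A reader might infer more, and three such readings are not supported:
- *Grade 3 instructions are irreconcilable.* Interrupting complies with both tables.
- *Grade 1 beyond 48 hours has no rule.* It fits neither row of Table 4-4, but the Grade 1 row of Table 4-3 has no time limit and covers it.
- *Section 4.4.1.17 repeats the Grade 4 conflict.* It says "Withhold treatment in subjects developing severe renal impairment (CTCAE version 4.03 grade 3 or 4) until renal toxicity is resolved". That gives no restart rule and waives nothing in Table 4-3.

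**What to change.** Amend the wording of Sections 4.3.1 (with Table 4-3), 4.3.2 and 4.4.1.1 (with Table 4-4):
1. Reconcile them so that each grade and duration of diarrhea has one action, including the Section 4.4.1.1 text against its own table.
2. State in Table 4-4 whether the two Grade 4 criteria of Table 4-3 apply before restart, and make Section 4.3.2 consistent with the answer.
3. Add a sentence to Section 4.3.1 saying whether the event-specific guideline or Table 4-3 prevails where they differ.
4. Correct the cross-reference in the note under Table 4-3.

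Which clinical rule to adopt is the sponsor's decision. The cost is a wording amendment with its approvals and notification of study staff. No procedures, visits or patients are added, and the sample size does not change.

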4.4.1.2 Hepatobiliary Disorders

Elevations of ALT, AST, and bilirubin have been observed during treatment with cabozantinib. Hepatic failure and hepatorenal syndrome, including fatal cases, can occur with erlotinib treatment in subjects with normal hepatic function; the risk of hepatic toxicity is increased in subjects with baseline hepatic impairment. Perform periodic liver testing (transaminases,

CONFIDENTIAL

bilirubin, and alkaline phosphatase) during treatment. If possible, hepatotoxic concomitant medications should be discontinued in subjects who develop increased values of ALT, AST, or bilirubin.

Subjects on this study may enter with increased ALT/AST serum levels up to $3 \times$ ULN. Dose reductions of study treatment should be considered in any subject who develops drug-related grade 2 bilirubin lasting longer than 1 week. In subjects who develop doubling of ALT/AST elevations in combination with a bilirubin elevation $> 2 \times$ ULN without reasonable other explanation, drug-induced liver injury should be suspected and treatment interrupted. Reinstitution of study treatment after recovery of ALT, AST, and bilirubin to baseline level is at the discretion of the investigator.

Withhold and consider discontinuing erlotinib in subjects without pre-existing hepatic impairment for total bilirubin levels greater than $3 \times$ the ULN or transaminases greater than $5 \times$ the ULN. Withhold and consider discontinuing erlotinib in patients with pre-existing hepatic impairment or biliary obstruction for doubling of bilirubin or tripling of transaminases values over baseline. Discontinue erlotinib in subjects whose abnormal liver tests meeting the above criteria do not improve significantly or resolve within 3 weeks.

4.4.1.3 Hematological Disorders

Hematological toxicities (i.e., neutropenia and thrombocytopenia) and associated complications have been observed after administration of cabozantinib and may be managed with dose interruptions and/or dose reductions. Use of granulocyte colony-stimulating factor support for neutrophil recovery is allowed per investigator discretion and in accordance with accepted guidelines after the first incidence of clinically relevant cytopenia.

Febrile neutropenia or evidence of infection associated with neutropenia should be treated appropriately and in a timely manner according to institutional guidelines.

Dose reductions or dose interruptions for anemia are not mandated but can be applied as clinically indicated. Supportive care such as red blood cell transfusions may be managed according to institutional guidelines.

4.4.1.4 Fatigue, Anorexia, and Weight Loss

Fatigue has been reported during treatment with cabozantinib and erlotinib. Refer to Table 4-3 for general management guidelines.

CONFIDENTIAL

Anorexia and weight loss should be managed in accordance to local standard of care including nutritional support. If fatigue, anorexia, or weight loss cannot be adequately managed, study treatment should be temporarily interrupted or dose reduced per Table 4-2 and Table 4-3.

4.4.1.5 Skin Disorders

Palmar-plantar erythrodysesthesia syndrome (PPES; also known as hand-foot syndrome), skin rash (including blisters, erythematous rash, macular rash, skin exfoliation, dermatitis acneiform, and papular rash), pruritus, dry skin, erythema, pigmentary changes, and alopecia have been reported in cabozantinib-treated subjects. Treatment guidelines for PPES related to study treatment are presented in Table 4-5.

Rash was amongst one of the most common adverse reactions experienced by $\geq 20\%$ of subjects who took erlotinib. Grade 3-4 rash was reported in 5% of patients treated with erlotinib and gemcitabine as first-line treatment of pancreatic cancer. Rash includes PPES, acne, skin disorder, pigmentation disorder, erythema, skin ulcer, dermatitis exfoliative, rash popular, and skin desquamation. Bullous, blistering and exfoliative skin conditions, including cases suggestive of Stevens-Johnson syndrome/toxic epidermal necrolysis, which in some cases were fatal, can occur with erlotinib treatment. Discontinue treatment in subjects who develop severe bullous, blistering or exfoliating conditions. Please refer to the guidelines for treatment-related rash (except for PPES which can be found in Table 4-5 below) in Table 4-3.

In the case of study treatment-related skin changes (e.g., rash, hand-foot syndrome), the investigator may request that additional assessments be conducted with the subject's consent. These assessments may include digital photographs of the skin changes and/or a biopsy of the affected skin and may be repeated until the skin changes resolve.

CONFIDENTIAL

Table 4-5: Management of Treatment-Emergent Hand-Foot Syndrome (PPES)

| CTCAE v.4.03 Grade | Action To Be Taken |
|---------------------------|--|
| Grade 1 | Study treatment may be continued at the current dose if PPES is clinically insignificant and tolerable. Otherwise, study treatment should be reduced to the next lower dose level. ^a Start urea 20% cream twice daily AND clobetasol 0.05% cream once daily. Reassess at least weekly; if PPES worsens at any time or does not improve after 2 weeks, proceed to the intervention guidelines for Grade 2. |
| Grade 2 | Study treatment may be continued if PPES is tolerated. Study treatment should be dose reduced or interrupted if PPES is intolerable. Continue urea 20% cream twice daily AND clobetasol 0.05% cream once daily and add analgesics (e.g., non-steroidal anti-inflammatory drug (NSAID)s/gamma-aminobutyric acid agonists) for pain control if needed. Reassess at least weekly; if PPES worsens or affects self-care, proceed to the intervention guidelines for Grade 3. |
| Grade 3 | Interrupt study treatment until severity decreases to Grade 1 or 0. Continue treatment of skin reaction with clobetasol 0.05% cream twice daily AND analgesics. Resume study drug at a reduced dose if PPES recovers to Grade ≤ 1 . Discontinue subject from study treatment if PPES does not improve within 6 weeks. |

^a Permitted dose levels are defined by individual protocols.

4.4.1.6 Wound Healing and Surgery

Surgical and traumatic wounds must have completely healed before starting cabozantinib treatment and be monitored for wound dehiscence or wound infection while the subject is being treated with cabozantinib. If possible, cabozantinib treatment should be stopped for at least 28 days prior to major surgery.

4.4.1.7 Hypertension

Hypertension is a common class effect of drugs that inhibit VEGF pathways and has been reported among subjects treated with cabozantinib.

Treatment guidelines for hypertension deemed related to cabozantinib are presented in Table 4-6. Blood pressure should be monitored in a constant position at each visit (either sitting or supine). In general, subjects with known hypertension should be optimally managed before study entry. Decisions to decrease or hold the dose of study treatment must be based on blood pressure readings taken by a medical professional and must be confirmed with a second measurement at least 5 minutes after the first measurement. Other than for hypertension requiring immediate therapy, the presence of new or worsened hypertension should be confirmed at a second visit before taking therapeutic action. It is recommended that this second visit occurs within 1 week.

CONFIDENTIAL

Treatment should be discontinued in subjects with hypertensive crises or hypertensive encephalopathy.

Table 4-6: Management of Hypertension Related to Cabozantinib

| Criteria for Dose Modifications | Treatment/Cabozantinib Dose Modification |
|--|--|
| Subjects NOT receiving optimized anti-hypertensive therapy | |
| > 150 mm Hg (systolic) ^a and < 160 mm Hg OR > 100 mm Hg (diastolic) and < 110 mm Hg | 
 Optimize antihypertensive medications by adding new or additional antihypertensive medications and/or increase dose of existing medications. Reduce study treatment by one dose level if optimal antihypertensive therapy (usually to include 3 agents) does not result in BP <150 mm Hg systolic or <100 mm Hg diastolic If subject is symptomatic interrupt study treatment |
| ≥ 160 mm Hg (systolic) OR ≥ 110 mm Hg (diastolic) | 
 Reduce cabozantinib by one dose level^b or interrupt study treatment per investigator discretion Add new or additional anti-hypertensive medications and/or increase dose of existing medications and monitor subject closely for hypotension. If optimized antihypertensive therapy (usually to include 3 agents) does not result in BP < 150 mm Hg systolic or < 100 mm Hg diastolic, study treatment should be dose reduced further or interrupted Study treatment should be dose interrupted if upper limits of systolic BP (≥ 160 mm Hg) are sustained and not adequately manageable or if systolic BP is > 180 mm Hg or diastolic BP > 110 mm Hg, or if subject is symptomatic Re-start study treatment at the most tolerable dose and re-escalate only if BP falls to and is sustained at < 150 mm Hg systolic and < 100 mm Hg diastolic |
| Hypertensive emergency ^c | 
 Discontinue study treatment |

^a The investigator may decide to initiate or adjust antihypertensive treatment at a lower threshold than systolic BP >150 or diastolic BP >100 based on their clinical judgment and assessment of the individual subject.

^b Permitted dose levels are defined by individual protocols.

^c Hypertensive emergency is defined as uncontrolled elevated blood pressure with clinical evidence of progressive or impending end-organ damage (eg, myocardial infarction/ischemia, intracranial hemorrhage, cerebral ischemia, pulmonary edema, encephalopathy, kidney damage).

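### Table 4-6 gives hypertension dose instructions that do not fit together: the diastolic interruption value, the test for controlled blood pressure and, to a lesser degree, the drug named

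*Combined protocol and SAP*

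**What the plan says.** Section 4.4.1.7 limits the table's scope: "Treatment guidelines for hypertension deemed related to cabozantinib are presented in Table 4-6". Below the row for hypertensive emergency, the table has two working rows.

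- **Milder row.** It is entered at "> 150 mm Hg (systolic) ^a and < 160 mm Hg OR > 100 mm Hg (diastolic) and < 110 mm Hg". Antihypertensives are optimized first. The next instruction is "Reduce study treatment by one dose level if optimal antihypertensive therapy" fails, failure being defined as therapy that "does not result in BP <150 mm Hg systolic or <100 mm Hg diastolic". Symptoms lead to interruption of study treatment.
- **Severe row.** It is entered at systolic 160 or more, or diastolic 110 or more, and has five bullets.
  1. "Reduce cabozantinib by one dose level", or interrupt study treatment, as the investigator judges.
  2. Add or increase antihypertensives.
  3. If the same 150-or-100 target is not reached, reduce study treatment further or interrupt it.
  4. Interrupt study treatment if a systolic pressure of 160 or more is sustained and cannot be managed, "or if systolic BP is > 180 mm Hg or diastolic BP > 110 mm Hg", or if there are symptoms.
  5. Restart at the best-tolerated dose, with dose increases allowed "only if BP falls to and is sustained at < 150 mm Hg systolic and < 100 mm Hg diastolic".

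**The concern.** Section 4.4.1.7 describes hypertension as a common class effect of drugs that inhibit VEGF pathways, so investigators can be expected to use this table. Two investigators faced with the same reading could act differently and each cite the table. With a diastolic pressure above 110, one could reduce cabozantinib under the first bullet and the other interrupt under the fourth. With one value still high on optimal therapy, one could reduce and the other continue at full dose. Patient safety is at stake, and so is consistency of exposure to the combination under test. Drug naming matters because Table 4-2 gives each drug its own reduction step (cabozantinib 40 to 20 mg, erlotinib 100 to 50 mg). The wording therefore decides whether erlotinib is reduced as well.

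**Working it through.** No sample-size or error-rate formula applies. The check sets the bullets side by side and evaluates their thresholds. S is systolic and D is diastolic pressure in mm Hg; all limits come from Table 4-6.

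**1. Diastolic limits in the severe row**

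- Entry on the diastolic criterion: D ≥ 110. First bullet: reduce cabozantinib or interrupt study treatment, at discretion.
- Fourth bullet: interrupt if D > 110.
- Values in the row that the fourth bullet does not cover: D ≥ 110 and not D > 110, which leaves D = 110 only.
- Same check on the systolic criterion: S ≥ 160 and not S > 180 leaves 160 to 180. Within that band, interruption depends on the pressure being sustained and unmanageable, or on symptoms.

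The choice to reduce without interrupting therefore has a real range on the systolic criterion and a single value on the diastolic one.

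**2. The test for controlled pressure**

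- Reading A, literal: the target is met if S < 150 or D < 100, so the reduction trigger is S ≥ 150 and D ≥ 100.
- Reading B, failing either limit: the target is met if S < 150 and D < 100, so the trigger is S ≥ 150 or D ≥ 100.
- The re-escalation bullet requires S < 150 and D < 100, which matches B.

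| Reading on optimized therapy | Target met under A | Target met under B |
|---|---|---|
| 155/95 | yes | no |
| 145/105 | yes | no |
| 155/105 | no | no |
| 170/90 | yes | no |
| 130/112 | yes | no |

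To see how far the readings diverge, take every whole-number pair with S from 120 to 200 and D from 70 to 130, which is 81 × 61 = 4,941 pairs.

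- Pairs below the severe row: 40 × 40 = 1,600. Severe row: 4,941 − 1,600 = 3,341.
- Milder row: 1,600 − 31 × 31 = 639.
- Milder row, target not met under A: 10 × 10 − 1 = 99 (150/100 is not in the row). Target met: 639 − 99 = 540.
- Severe row, target not met under A: 51 × 31 − 100 = 1,481. Target met: 3,341 − 1,481 = 1,860.
- Under B, none of the 639 or the 3,341 meets the target, since every pair has at least one value over its limit.

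These are counts of possible readings, not shares of patients. They show that under A most readings that qualify for the milder row, and more than half of those in the severe row, already count as controlled.

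The consequence differs by row. In the severe row, the first and fourth bullets still offer or direct a dose action at 170/90 or 130/112. The milder row has no such backstop for a patient without symptoms.

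**3. Drug named**

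| Dose action | Milder row | Severe row |
|---|---|---|
| First-step reduction | none (antihypertensives first) | cabozantinib |
| Reduction after failed control | study treatment | study treatment |
| Interruption | study treatment | study treatment |
| Restart | not stated | study treatment |

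The one action confined to a single drug is the first-step reduction in the severe row.

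**The case against.** The strongest reply is that a sensible investigator can follow the table as it stands.

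- **Conjunction.** The phrase is negated, and taking it as failing either limit is natural. The bullets then agree with the either-value row entry, with the re-escalation bullet and with exclusion criterion 12(a)(ii), which treats hypertension as uncontrolled when either value is above its limit. The bullets also govern different decisions, reduction in one case and re-escalation in the other. This stands as a reason not to call the wording a proven contradiction. It does not remove the ambiguity, because the literal reading is also available and leads to a different dose action.
- **Diastolic limit.** The text says treatment should be interrupted, in a table introduced as guidelines, so calling the hold mandatory would go too far. Interrupting above 110 satisfies both bullets, and the fourth can be read as a specific limit on the first. Even so, the first bullet offers reduction alone as an equal choice, and nothing says that it lapses above 110.
- **Discretion elsewhere.** Section 4.3.1 allows reduction or interruption at lower grades on the investigator's judgment, and footnote a of the table allows earlier antihypertensive treatment. These soften the consequence but do not say which instruction applies.
- **Drug scope.** A reader might infer that milder hypertension cuts erlotinib while severe hypertension leaves it at full dose. The table does not say that. The milder reduction follows only failed control, and at that point the severe row also acts on study treatment, as do its interruption and restart instructions. Table 4-3 also allows one drug to be modified when it is the suspected cause. Only uneven naming in one first-step bullet remains.

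**Conclusion.** The point holds as a drafting problem that bears on safety. The diastolic mismatch is firm: the first and fourth bullets of the severe row differ for every diastolic value in the row except exactly 110. The conjunction is a real ambiguity in a dose-reduction trigger. It matters most in the milder row, where an asymptomatic patient staying at 155/95 or 145/105 is reduced under one reading and not under the other. The drug naming is a lesser inconsistency.

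These conclusions rest on the table's wording alone. A reader might want the share of patients affected, but the documents give no distribution of on-treatment blood pressure, so no percentage is offered. A reader might also infer that a patient at 170/95 on optimized therapy receives no dose action. That is not supported, because the severe row's first bullet applies and its fourth covers sustained, unmanageable systolic pressure. The two-stage design, its sample size, power and alpha are untouched.

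**What to change.** Within Table 4-6, the sponsor should:

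1. reconcile the diastolic entry instruction with the diastolic interruption instruction in the severe row, so that each reading leads to one stated action or one stated choice;
2. use one unambiguous definition of controlled blood pressure in both reduction bullets and the re-escalation bullet, stating whether one or both values must be below their limits;
3. name the affected drug or drugs consistently in the two rows, or state why they differ.

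The clinical team decides every threshold and the drug scope; this review takes no position on them. The change is a text edit to one table and adds no visits, measurements or patients.
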